### **1.2.5 Potential Toxicities**

Voclosporin has been studied in numerous disease states. When examining LN, there were a small proportion of voclosporin treated subjects that experienced an early drop of  $\geq 30\%$  in eGFR, however that proportion then remains stable over time. None of these treatment-emergent adverse events (TEAEs) were classed as serious. The majority of TEAEs of decreased GFR were classed as mild or moderate, and resulted in permanent discontinuation of study drug in 1 (1.1%) placebo subject, 7 (7.9%) voclosporin low-dose subjects and

5 (5.7%) voclosporin high-dose subjects. There were more TEAEs of hypertension seen in the voclosporin-treated patients compared to placebo however, overall mean systolic and diastolic BP decreased in all groups, without statistically significant differences seen between groups. Overall, only 1 (1.1%) subject, in the voclosporin high-dose group, had a TEAE of hypertension that resulted in permanent discontinuation of study drug.

There was evidence of an increased incidence of TEAEs over placebo and with increased dose of voclosporin in the System Organ Classes of Infections and Infestations, Gastrointestinal (GI) Disorders, and Vascular Disorders.

There were more deaths in the voclosporin low-dose arm (10) than in either the voclosporin high-dose (2) or placebo (1) arms, with the majority (11/13) occurring in South-East Asia. All deaths were assessed by the Investigator and Data and Safety Monitoring Board (DSMB) as unrelated to study treatment. A full description of AEs can be found in the IB.

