## 7.9 Increased Blood Pressure

For all subjects, the target systolic pressure is  $\leq 130$  mmHg and the target diastolic pressure is  $\leq 80$  mmHg. Investigators should use all means possible permitted in the protocol to maintain the BP within these limits. If no further adjustment of antihypertensive therapy is possible, the subject should be discussed with the Medical Monitor.

If on any study day, systolic BP is  $>165$  mmHg or diastolic BP is  $>105$  mmHg and is associated with symptoms of hypertension (i.e., persistent headache, altered mental status, shortness of breath, chest pain consistent with angina pectoris, symptoms of heart failure, evidence of renal insufficiency of new onset, evidence of hypertensive retinal injury [hemorrhages, papilledema]), study treatment should be withheld, the Medical Monitor contacted, and the subject treated as per Investigator local practices and best judgment. The subject will continue with all study visits per the [Schedule of Events](#). Study treatment must not be reintroduced without prior discussion with the Medical Monitor.

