## **Appendix 2 Measurement of Blood Pressure**

1. Whenever possible, BP measurements should be undertaken by the same study site personnel at each clinic visit.
2. Whenever possible, the BP determinations should be undertaken at approximately the same time of day for each study visit and at the same time in relation to prior study treatment ingestion.
3. The measurements should be undertaken prior to blood collection.
4. Prior to measuring BP, the study subject should be seated in a quiet room for at least 5 minutes, in a chair with his/her back supported and feet comfortably resting on the floor.
5. Due to the likelihood each arm can have a slightly different BP, it is strongly encouraged to use the same arm for all measurements, supported at heart level.
6. No restrictive clothing should encircle the arm in which BP measurements are determined.
7. An appropriately sized cuff will be required wherein the cuff bladder encircles at least 80% of the upper portion of the arm.
8. Three serial BP readings will be undertaken with a minimum of 2 minutes between readings and with the cuff fully deflated between each determination.
9. The mean of the second and third of these 3 readings will be used as the study day BP value.
10. All measurements, along with the calculated mean value, will be recorded in the source documents. The mean of the second and third readings will be calculated within the EDC as the study day result.

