## Appendix 6 Expanded List of Allowed Concomitant Medications

- Prophylactic therapy for steroid-induced bone loss (calcium with Vitamin D and/or a bisphosphonate).
- Low dose aspirin is allowed for cardiovascular prophylaxis.
- Minor GI AEs (such as nausea, vomiting and diarrhea) may be treated symptomatically (e.g., with loperamide for diarrhea or standard anti-emetics such as metoclopramide or domperidone for nausea and vomiting). Proton pump inhibitors or ranitidine are permitted for dyspepsia or gastric protection. Magnesium or aluminum containing antacids may be used, but should not be taken at the same time as study treatment; such antacids, if required, should be taken either 1 hour before or 2 hours after study treatment.
- Amphotericin or oral nystatin are permitted as infective prophylaxis against fungal infections, and low-dose sulfamethoxazole/trimethoprim is permitted as prophylaxis against *Pneumocystis carinii pneumonia*.
- Granulocyte colony stimulating factor is allowed to manage neutropenia in the presence of major infection (i.e., infections requiring IV antibiotics).
- Oral or IV iron preparations for iron deficiency and/or anemia.
- Erythropoietin is permitted for treatment of severe anemia (hemoglobin <10 mg/dL).
- Cytomegalovirus prophylaxis is permitted for example with oral valganciclovir.
- Acute intermittent administration of NSAIDs for not greater than 7 consecutive days is permitted.
- Lipid-lowering therapies (e.g., statins) will be used as clinically indicated.
- Antimalarials should be prescribed when clinically indicated.
- Angiotensin-converting enzyme inhibitors, ARBs, and aliskerin and other therapies are recommended, as per standard guidelines but if used their dose must be stable throughout the study. In addition subjects must be on a stable dose of ACE inhibitors or ARBs for 4 weeks prior to enrollment.
- In the case of uncontrolled hypertension (systolic BP >165 mmHg or diastolic >105 mmHg on 2 successive measurements), the addition of a diuretic or calcium channel blocker only are permitted, together with dose decreases or

[figure not shown]
interruption of study treatment per the instructions in Section 7.9, [Increased Blood Pressure](#).

[figure not shown]

[figure not shown]

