6.2.18 Short Form Health Survey (SF-36)

The SF-36 HRQoL assessment is a 36-question subject HRQoL questionnaire. The SF-36 responses will be weighted as follows:

Item number	Original Response	Weight
1, 2, 20, 22, 34, 36	1 →	100
	2 →	75
	3 →	50
	4 →	25
	5 →	0
3, 4, 5, 6, 7, 8, 9, 10, 11, 12	1 →	0
	2 →	50
	3 →	100
13, 14, 15, 16, 17, 18, 19	1 →	0
	2 →	100
21, 23, 26, 27, 30	1 →	100
	2 →	80
	3 →	60
	4 →	40
	5 →	20
	6 →	0

QMD Ref: [REDACTED]	Effective: 12Aug2019	Governing QMD: [REDACTED]
Confidentiality Statement		
This document is the property of [REDACTED] and may not be duplicated, copied, altered or removed from company without prior approval from [REDACTED] or in compliance with [REDACTED].		

REF: [REDACTED]

		Controlled Quality Management Document	
		Sponsor:	Aurinia Pharmaceuticals
		Protocol Number:	AUR-VCS-2016-02
STATISTICAL ANALYSIS PLAN. PHASE 2-3-4			

Item number	Original Response	Weight
24, 25, 28, 29, 31	1 →	0
	2 →	20
	3 →	40
	4 →	60
	5 →	80
	6 →	100
32, 33, 35	1 →	0
	2 →	25
	3 →	50
	4 →	75
	5 →	100

These items will be further grouped into the following scales:

Scales	Number of items	Mean of Items
Physical functioning	10	3, 4, 5, 6, 7, 8, 9, 10, 11, 12
Role limitations due to physical health	4	13, 14, 15, 16
Role limitations due to emotional problems	3	17, 18, 19
Energy/fatigue	4	23, 27, 29, 31
Emotional well-being	5	24, 25, 26, 28, 30
Social functioning	2	20, 32
Pain	2	21, 22
General health	5	1, 33, 34, 35, 36
Total mean score	36	All 36 items

QMD Ref: [REDACTED]	Effective: 12Aug2019	Governing QMD: [REDACTED]
Confidentiality Statement		
This document is the property of [REDACTED] and may not be duplicated, copied, altered or removed from company without prior approval from [REDACTED] or in compliance with [REDACTED].		

REF: [REDACTED]

		Controlled Quality Management Document	
		Sponsor:	Aurinia Pharmaceuticals
		Protocol Number:	AUR-VCS-2016-02
STATISTICAL ANALYSIS PLAN. PHASE 2-3-4			

Each scale will be calculated for each subject by taking the mean of its corresponding item.

Only scheduled post-baseline laboratory and vital signs values will be tabulated. Post-baseline repeat / unscheduled assessments will be disregarded, although these post-baseline assessments will be listed in the relevant appendices to the CSR.

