6.3 Conventions

All data listings, summaries, figures and statistical analyses will be generated using SAS version 9.4 or higher¹.

Summaries will be presented by treatment group for all subjects. Treatment group labels will be displayed as follows:

- Placebo
- Voclosporin
- Overall

Columns to be included within the table shells are as follows:

Demography	Treatment group and overall
Baseline	Treatment group and overall
Disposition	Treatment group and overall
Efficacy	Treatment group
TEAEs	Treatment group
Other safety	Treatment group

Tables of events or medications will be ordered in descending frequency of subjects followed by (where applicable) events for the system organ class (or Anatomical Therapeutic Chemical Classification System [ATC] level 2 for medications) followed by the preferred term. Ordering will be for the voclosporin treatment group first followed by the placebo group and alphabetical thereafter.

Listings will be sorted in the following order: treatment group, subject, parameter, and visit unless otherwise stated. All data will be listed.

Continuous variables will be summarized by the number of non-missing observations, mean, median, standard deviation, and minimum and maximum. For all tabulations of changes from baseline data, the lower and upper 95% confidence limits for the mean for the individual treatments will be given.

QMD Ref: [REDACTED]	Effective: 12Aug2019	Governing QMD: [REDACTED]
Confidentiality Statement		
This document is the property of [REDACTED] and may not be duplicated, copied, altered or removed from company without prior approval from [REDACTED] or in compliance with [REDACTED].		

		Controlled Quality Management Document	
		Sponsor:	Aurinia Pharmaceuticals
		Protocol Number:	AUR-VCS-2016-02
STATISTICAL ANALYSIS PLAN. PHASE 2-3-4			

Categorical variables will be summarized by presenting the frequency and percent. Percentages will be based on the number of non-missing observations out of the subject population unless otherwise specified. For each variable, all categories will be shown. Zero frequencies (but not the percent) within a category will be presented.

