6.12.3 Vital Signs

Descriptive statistics for observed values and changes from baseline in the following vital signs will be presented by treatment group and visit:

- Systolic blood pressure (mmHg)
- Diastolic blood pressure (mmHg)
- Pulse rate (bpm)
- Body temperature (degrees Celsius).

Mean values for systolic and diastolic blood pressure will be used in the summary tables. Where the mean value is unavailable, an individual measure at the visit in question will be used.

Listings of all vital sign measurements will be provided.

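### No table counts, by arm, the subjects whose measured blood pressure exceeds the protocol's limits or who start or increase an antihypertensive; by-visit summaries under treat-to-target can understate a drug effect

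*SAP*

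**What the plan says.** **Planned analysis.** SAP 6.12.3 gives: "Descriptive statistics for observed values and changes from baseline in the following vital signs will be presented by treatment group and visit". SAP 6.3 defines the content: "Continuous variables will be summarized by the number of non-missing observations, mean, median, standard deviation, and minimum and maximum". All vital signs are also listed. Where 6.12.3 adds "Mean values for systolic and diastolic blood pressure will be used in the summary tables", this most naturally means each subject's averaged readings, matching Protocol Appendix 2: "The mean of the second and third of these 3 readings will be used as the study day BP value".

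**Management of BP.** Protocol 7.9 sets targets of 130 systolic and 80 diastolic for all subjects and adds: "Investigators should use all means possible permitted in the protocol to maintain the BP within these limits". Section 9.1.3.1 calls for management once a value above 130/80 is confirmed. Section 9.2.5 asks for an unscheduled visit when BP is high.

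**Unscheduled readings.** The closing paragraph of SAP 6.2.18, although under the SF-36 heading, says: "Only scheduled post-baseline laboratory and vital signs values will be tabulated". SAP 6.2.12 instead maps unscheduled visits to the nearest scheduled one and tabulates the latest observation.

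**Prior experience.** Protocol 1.2.5 reports more hypertension TEAEs on voclosporin in Phase 2, yet "overall mean systolic and diastolic BP decreased in all groups, without statistically significant differences seen between groups".

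**The concern.** Safety is the primary objective, and Protocol 2.1 names BP, with renal function, as a dose-related risk managed through dose. When both arms are treated to the same target, part of any pressor effect appears as extra antihypertensive treatment instead of higher pressure at the visit. Arm-level visit statistics then show the drug effect net of the response to it. A count of subjects who crossed a limit, and of those who needed more treatment, would show what the visit averages absorb. The SAP already gives laboratory values range classes and shift tables, and ECG interpretation shift tables; measured BP gets neither. What is at stake is the strength of the objective evidence on a known risk, because the remaining by-arm evidence depends largely on what investigators report as an adverse event.

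**Working it through.** The plan states no BP figure to reproduce. The check is a reading of the text followed by an illustration.

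**1. What each planned output can show**
- Mean, median and SD by visit: location and spread after treatment.
- Maximum by arm and visit: one subject's extreme, not how many crossed.
- TEAE tables: hypertension as reported. The rule in Protocol 10.2.5 on shifts to pathological values covers laboratory tests; nothing found makes a BP crossing an AE automatically.
- Medications at ATC Level 2: drug groups by arm. Those started in AURORA 2 are defined separately, but dose increases and the reason for starting are not isolated.

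**2. What happens to the highest reading.** Take a subject with a scheduled value above target, a recall value above 165, and a later recall value back below target, all nearest the same visit. Under 6.2.18 the table holds the first; under 6.2.12 it holds the last. Under neither does it hold the highest.

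**3. Illustration.** All inputs are assumptions.

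*Model A.* Placebo systolic level N(124, SD 13), reading error SD 6, drug effect +6 mmHg. After a reading above 130, the later level is max(level − 12, 122).
- Mean difference after one round of treatment: 4.0 mmHg; 4.0/6 = 67% survives.
- Above 130 at one reading after treatment: 30% v 20%, or 10 points.
- Treatment repeated over 12 visits: above 130 at any of the 12, 77% v 61% (16 points); at any of the last 8, 49% v 39% (10 points).

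*Model B.* Placebo N(122, between-subject SD 11), within-subject SD 8, 8 visits. Each reading above 130 adds an 8 mmHg treatment step, to a maximum of 3.

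| Effect | Last-visit mean difference, untreated | Treated to target | Surviving | Ever above 130, treated |
|---|---|---|---|---|
| +5 | 5.05 | 1.87 | 1.87/5.05 = 37% | 75.6% v 61.1% |
| +8 | 7.90 | 2.92 | 2.92/7.90 = 37% | 82.9% v 61.0% |

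With 108 per arm assumed (216/2; the SAP gives no split) and SD 15, power for the +5 mean difference falls from 0.70 to 0.15. For ever above 130 it stays at about 0.65 to 0.63.

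**4. Reading the models**
- A count from the start of follow-up is almost immune to treatment by construction, because treatment follows the first crossing.
- A count starting after a year on treatment, as in AURORA 2 alone, is not immune: Model A drops from 16 to 10 points. Hence the need for both periods.
- Crossings of 165 are rare. In Model B at +5 they fall on voclosporin from 1.4% untreated to 0.3% treated, so that limit alone detects little.

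**5. Precision.** For 49% v 39% at 108 per arm, the 95% half-width is 1.96 × √[(0.49×0.51 + 0.39×0.61)/108] = 0.13. A 10-point difference would carry an interval of about −3 to 23 points. The table is descriptive, not a test.

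**The case against.** The strongest reply is that the harm is already counted by arm. The SAP tabulates TEAEs by preferred term, severity, seriousness, dose modification, discontinuation and year of onset, with exposure-adjusted rates over both studies. The Phase 2 signal in Protocol 1.2.5 was found by just that route, and was reported beside the means. This stands, and it limits the point: a reader might infer that hypertension goes uncounted by arm, and the documents do not support that. They support only that measured crossings are not counted.

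A reader might also infer that BP is reduced to arm means, or that treatment to target erases the drug effect. Neither holds. Median, SD, minimum and maximum are planned, and both models leave part of the mean difference in place.

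Three further objections have force. Threshold counts are also diluted by treatment once it has begun. Any value above 130/80 over many visits will mark a large share of both arms. Adding unscheduled readings gives more chances to subjects already high, since high BP prompts those visits. These argue for showing the counts in more than one way, not for omitting them.

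**Conclusion.** The gap is real and moderate. In the available SAP text, measured BP has by-visit descriptive statistics and listings only. Limit crossings and antihypertensive starts or increases are not counted by arm, and neither rule on unscheduled readings keeps the highest value. Visit summaries can therefore understate a pressor effect, leaving detection mainly to reported TEAEs with a partial supplement from medication tables.

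The models agree on direction; the loss in the mean difference, from about 33% (Model A, one round) to 63% (Model B), depends entirely on assumed variability and treatment response. It would go too far to predict that the study will show no BP difference, or that the report would offer the visit means as reassurance.

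One caveat applies: the SAP text immediately before 6.12.3, and from 6.11.8 into 6.12.1, was not available, so absence is judged without it.

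**What to change.** In SAP 6.12.3 add, by arm, for AURORA 2 and for Month 0-36:
- number and percent of subjects with any post-baseline study-day BP above 130 systolic or 80 diastolic, and above 165 systolic or 105 diastolic, with relative risk, 95% CI and follow-up time or an exposure-adjusted rate;
- each count twice: scheduled visits only, and all values including unscheduled and repeat;
- number and percent who started or increased an antihypertensive after baseline.

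Exempt these worst-value tables from 6.2.18, and reconcile 6.2.12 with 6.2.18 for unscheduled vital signs. Keep the by-visit summaries.

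The limits above are the protocol's own; no clinical threshold is proposed here. The sponsor must reconcile their wordings first. Section 7.9 uses strictly above 165 or 105 with symptoms; 9.2.5 uses at or above; Appendix 6 has "uncontrolled hypertension (systolic BP >165 mmHg or diastolic >105 mmHg on 2 successive measurements". The 130/80 target in 7.9 also sits beside a 140/90 goal in Appendix 1.

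The cost is SAP wording and a few tables from data already collected. The downside is small: counts above 130/80 will be high in both arms and rise with the number of readings, so follow-up time and the scheduled-only version belong beside them.

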6.12.4 Electrocardiogram Data

Descriptive statistics for observed values and changes from baseline as recorded in the AURORA 1 database for subjects that did not participate in AURORA 2, and as recorded in the AURORA 2 database for subjects that did participate in AURORA 2 in the following ECG variables at Months 6, 12, 18, 24, and 36, will be tabulated at each follow-up:

- Heart rate (bpm)
- PR interval (ms)
- QRS complex (ms)
- QT interval (ms)
- QTc interval (ms)
- QTcF interval (ms)

Shift tables in relation to the overall interpretation (Normal, Abnormal NCS, and Abnormal CS) from baseline to each follow-up visit will be presented. Listings of all ECG measurements will be provided.

6.12.5 Physical Examination

Physical examination will be summarized for the safety population at timepoints: Month 12 and 36. The following parameters will be summarized: Height (as part of demography at screening only) and Weight.

Physical examination results with clinically significant abnormalities (Yes/No) will be listed.

QMD Ref: [REDACTED]	Effective: 12Aug2019	Governing QMD: [REDACTED]
Confidentiality Statement		
This document is the property of [REDACTED] and may not be duplicated, copied, altered or removed from company without prior approval from [REDACTED] or in compliance with [REDACTED].		

REF: [REDACTED]

		Controlled Quality Management Document	
		Sponsor:	Aurinia Pharmaceuticals
		Protocol Number:	AUR-VCS-2016-02
STATISTICAL ANALYSIS PLAN. PHASE 2-3-4			

7 INTERIM ANALYSIS

The study will be ongoing during regulatory interaction and as such, regular reporting events will be required to ensure authorities are provided the most up to date information available.

These reporting events will incorporate both safety and efficacy analyses.

Timing of the interim analyses will range from 3 months post the final subject final visit of the AURORA 1 study (i.e., when the last subject reaches Month 15 of the AURORA 2 continuation study) up to 6 months prior to the end of AURORA 2 (i.e., when the last subject reaches Month 30 of the AURORA 2 continuation study).

8 DATA SAFETY MONITORING BOARD ANALYSIS

Data presentations for the Data and Safety Monitoring Board (DSMB) deliverables are provided in a separate SAP.

9 CHANGES TO PLANNED PROTOCOL ANALYSIS

Additional analyses will be performed to compare subjects who did not participate in AURORA 2 with those who participated.

Protocol stated: “Subjects who receive treatment from more than 1 arm will be assigned to the Orelvo arm.” And this was updated to “Subjects who receive voclosporin treatment for more than 14 days will be assigned to the voclosporin arm irrespective of the arm they were randomized to”.

Protocol did not mention covariates for MMRM analysis. In addition to baseline covariate the following covariates will be included in the model: biopsy class, MMF use at baseline, region.

QMD Ref: [REDACTED]	Effective: 12Aug2019	Governing QMD: [REDACTED]
Confidentiality Statement		
This document is the property of [REDACTED] and may not be duplicated, copied, altered or removed from company without prior approval from [REDACTED] or in compliance with [REDACTED].		

REF: [REDACTED]

		Controlled Quality Management Document	
		Sponsor:	Aurinia Pharmaceuticals
		Protocol Number:	AUR-VCS-2016-02
STATISTICAL ANALYSIS PLAN. PHASE 2-3-4			

